6.0 TREATMENT WITH CPI-613

CPI-613 will be administered to patients as shown in Table 6-1 (below). Briefly, a treatment cycle is 4 weeks, with CPI-613 given on Days 1 and 4 of the first 3 weeks. CPI-613 will also be given for 5 consecutive days a week before the start of Cycle 1, and this Pre-Cycle 1 treatment will only be given once in each patient. During Pre-Cycle 1 and each treatment cycle, patients will be treated with CPI-613 at the same dose, unless dose modification is warranted (see Section 6.2).

Table 6-1: Administration of CPI-613 in Patients with Advanced Cholangiocarcinoma

Treatment Cycle			Administration of CPI-613
	Week	Day	
Pre-Cycle 1 (1 week)	1	1	2-hr IV infusion via a central venous catheter
		2	2-hr IV infusion via a central venous catheter
		3	2-hr IV infusion via a central venous catheter
		4	2-hr IV infusion via a central venous catheter
		5	2-hr IV infusion via a central venous catheter
Cycle 1 (4 weeks)	1	1	2-hr IV infusion via a central venous catheter
		4	2-hr IV infusion via a central venous catheter
	2	1	2-hr IV infusion via a central venous catheter
		4	2-hr IV infusion via a central venous catheter
	3	1	2-hr IV infusion via a central venous catheter
	4	2-hr IV infusion via a central venous catheter	
Cycle 2 (4 weeks)	1	1	2-hr IV infusion via a central venous catheter
		4	2-hr IV infusion via a central venous catheter
	2	1	2-hr IV infusion via a central venous catheter
		4	2-hr IV infusion via a central venous catheter
	3	1	2-hr IV infusion via a central venous catheter
	4	2-hr IV infusion via a central venous catheter	
Etc. up to a total of 12 cycles ^a			

hr = hour; IV = intravenous; min = minutes.

^a Additional cycles can be given if the investigator considers it beneficial to do so.

6.1 Dose Levels, Dose Escalation, Sample Size and Justification of the Dose

6.1.1 Dose Levels, Dose Escalation and Sample Size

The dose levels to be used in assessing the safety and anti-cancer activities of CPI-613 in 10 patients with advanced bile duct cancers will be determined from a dose-escalation scheme using cohorts of patients with advanced bile duct cancers, as described below. The dose-escalation scheme is based on the number of patients exhibiting dose-limiting toxicity (DLT), and DLT is defined as toxicity of Grade 3 or higher attributed as probably or definitely related to CPI-613. The DLT determining period for all cohorts in the dose-escalation scheme is through the first cycle.

Comprehensive Cancer Center of Wake Forest University
A Pilot Study: Open-Label Clinical Trial of CPI-613 in Patients with Advanced Bile Duct
Cancers
CCCWFU # 59212

Cohort 1: The first 3 patients will not be treated with the 5 daily doses of CPI-613 during the pre-Cycle 1 week, and will only be treated with 3-weeks-on-1-week-off treatment cycles (see Table 6-1). The dose of CPI-613 will be 2,300 mg/m² (which is approximately three-quarters of the target dose). If none of these 3 patients develop a dose-limiting toxicity (DLT) through Cycle 1, the dose for the 3-weeks-on-1-week-off treatment cycles will be 3,000 mg/m² in all subsequent patients in this trial. However, if a DLT is observed in a patient (whether it is the 1st, 2nd or 3rd of the 3 intended patients), the number of patients in this cohort will be expanded to a maximum of 6 patients. If no DLT is observed in another patient out of a maximum of 6 patients, the dose for the 3-weeks-on-1-week-off treatment cycles will be 3,000 mg/m² in all subsequent patients in this trial. However, once DLT is observed in 2 patients, no additional patients will be treated at 2,300 mg/m² for the 3-weeks-on-1-week-off treatment cycles from that point on, even though the total number of patients in this cohort is as few as 2. The dose level of 2,300 mg/m², which induces a DLT in 2 or more patients, is considered to be above the maximum tolerated dose (MTD) for the 3-weeks-on-1-week-off treatment cycles. In this case, all subsequent patients in this trial will be treated at 1,700 mg/m² for the 3-weeks-on-1-week-off treatment cycles.

Cohort 2: In another 3 patients, the dose of CPI-613 for the 3-weeks-on-1-week-off treatment cycles will be as determined from Cohort 1. These patients will also be treated with the 5 daily doses of CPI-613 during the pre-Cycle 1 week. The dose of CPI-613 for the pre-Cycle 1 week will be 1,200 mg/m²/day, which has previously been established to be the weekly MTD (see Section 6.1.2). If none of these 3 patients develop a DLT, the study can move onto Cohort 3.

However, if a DLT is observed in a patient (whether it is the 1st, 2nd or 3rd of the 3 intended patients), the number of patients in this cohort will be expanded to a maximum of 6 patients. If no DLT is observed in another patient out of a maximum of 6 patients, the study will move onto Sub-Cohort 2 (see below). However, if a DLT is observed in 2 patients, no additional patients will be treated at 1,200 mg/m²/day during the pre-Cycle 1 week even though the total number of patients at this cohort is as few as 2. The dose level of 1,200 mg/m²/day during the pre-Cycle 1 week, which induces a DLT in 2 or more patients, is considered to be above the MTD for the pre-Cycle 1 week. In this case, the dose of CPI-613 for the pre-Cycle 1 week in subsequent patients in this trial will be 600 mg/m²/day (or 3,000 mg/m²/week, equivalent to the MTD when given as a single dose).

Sub-Cohort 2: Sub-Cohort 2 is activated only if 1 out of 6 patients exhibits DLT in Cohort 2. There are 3 patients in this sub-cohort, the dose of CPI-613 for the 3-weeks-on-1-week-off treatment cycles will be as determined from Cohort 1. These patients will also be treated with the 5 daily doses of CPI-613

Comprehensive Cancer Center of Wake Forest University
A Pilot Study: Open-Label Clinical Trial of CPI-613 in Patients with Advanced Bile Duct
Cancers
CCCWFU # 59212

during the pre-Cycle 1 week. The dose of CPI-613 for the pre-Cycle 1 week will be 1,700 mg/m²/day. If none of these 3 patients develop a DLT, the study can move onto Cohort 3. However, if a DLT is observed in a patient (whether it is the first, second or third of the 3 intended patients), the number of patients in this cohort will be expanded to a maximum of 6 patients. If no DLT is observed in another patient out of a maximum of 6 patients, the study will move onto Cohort 3. However, if a DLT is observed in 2 patients, no additional patients will be treated at 1,700 mg/m²/day during the pre-Cycle 1 week even though the total number of patients at this sub-cohort is as few as 2. The dose level of 1,700 mg/m²/day during the pre-Cycle 1 week, which induces a DLT in 2 or more patients, is considered to be above the MTD for the pre-Cycle 1 week. In this case, the dose of CPI-613 for the pre-Cycle 1 week in subsequent patients in this trial will be 600 mg/m²/day (or 3,000 mg/m²/week, equivalent to the MTD when given as a single dose).

Cohort 3: This cohort will be performed only if DLT is observed in Cohort 2, or DLT is observed in 1 or less patients in Sub-Cohort 2. There are 3 patients in this cohort, and the dose of CPI-613 for the 3-weeks-on-1-week-off treatment cycles will be as determined from Cohort 1. The dose for the 5 daily IV infusions during the pre-Cycle 1 week will be 2,300 mg/m²/day. If none of these 3 patients develop a DLT, the study can move onto Cohort 4. However, if a DLT is observed in a patient (whether it is the 1st, 2nd or 3rd of the 3 intended patients), the number of patients in this cohort will be expanded to a maximum of 6 patients. If no DLT is observed in another patient out of a maximum of 6 patients, the study will move onto Cohort 4. However, if a DLT is observed in 2 patients, no additional patients will be treated at 2,300 mg/m²/day during the pre-Cycle 1 week even though the total number of patients at this sub-cohort is as few as 2. The dose level of 2,300 mg/m²/day during the pre-Cycle 1 week, which induces a DLT in 2 or more patients, is considered to be above the MTD for the pre-Cycle 1 week. In this case, the dose of CPI-613 for the pre-Cycle 1 week in subsequent patients in this trial will be 1,700 mg/m²/day.

Cohort 4: This cohort will be performed only if DLT is observed in 1 or less patients in Cohort 3. There are 3 patients in this cohort, and the dose of CPI-613 for the 3-weeks-on-1-week-off treatment cycles will be as determined from Cohort 1. The dose for the 5 daily IV infusions during the pre-Cycle 1 week will be 3,000 mg/m²/day. If none of these 3 patients develop a DLT, the study can move onto Cohort 5. However, if a DLT is observed in a patient (whether it is the first, second or third of the 3 intended patients), the number of patients in this cohort will be expanded to a maximum of 6 patients. If no DLT is observed in another patient out of a maximum of 6 patients, the study will move onto Cohort 5. However, if a DLT is observed in 2 patients, no additional patients will be treated at 3,000 mg/m²/day during the pre-Cycle 1 week even though the total number of patients at this cohort is as few as 2. The dose level of 3,000

Comprehensive Cancer Center of Wake Forest University
A Pilot Study: Open-Label Clinical Trial of CPI-613 in Patients with Advanced Bile Duct
Cancers
CCCWFU # 59212

mg/m²/day during the pre-Cycle 1 week, which induces a DLT in 2 or more patients, is considered to be above the MTD for the pre-Cycle 1 week. In this case, the dose of CPI-613 for the pre-Cycle 1 week in subsequent patients in this trial will be 2,300 mg/m²/day

Cohort 5: This cohort is performed once the dose of CPI-613 for the 3-weeks-on-1-week-off treatment cycles has been determined from Cohort 1, and once the dose of CPI-613 for the pre-Cycle 1 week has been determined from Cohort 2-4. There are 10 patients in this cohort. These patients will be treated with CPI-613 for 5 days during the pre-Cycle 1 week at doses as determined from Cohorts 2-4, and the dose of CPI-613 for the 3-weeks-on-1-week-off treatment cycles will be as determined from Cohort 1.

6.1.2 *Justification of the Dose*

Based on Phase I trials in patients with solid tumors and hematologic malignancies, 3,000 mg/m² is the MTD, when CPI-613 is given as a single agent infused over 2 hours on Days 1 and 4 for 3 weeks of a 4-week treatment cycle. CPI-613 did not induce any significant adverse effects at or below MTD. Additionally, CPI-613 at or below 3,000 mg exhibits anti-tumor activities in patients with various types of solid and hematologic malignancies (Pardee et al, 2011a and b, & 2012; Lee et al. 2011 & 2012; Senzer et al 2012). Because of the safety and efficacy against other cancers, 3,000 mg/m² is the target dose for this pilot study.

In this study, patients will be treated with CPI-613 for 5 consecutive days during pre-Cycle 1, prior to being treated with CPI-613 given 2x weekly for 3 weeks. A sub-MTD (2,300 mg/m², approx. three-quarters of the MTD) will be used in the first 3 patients (in Cohort 1) who will be treated with the 4-week treatment cycles and without treatment during the pre-Cycle 1 week to ensure safety, before initiating the dose escalation procedure to determine the MTD. The maximum plasma concentration (C_{max}) of CPI-613 associated with the dose level of 2,300 mg/m² is ~90 µM, which is significantly lower than the C_{max} of ~200 µM associated with 3,000 mg/m². Therefore, 2,300 mg/m² is expected to be a safe starting dose.

After determining the dose to be used in 3-weeks-on-1-week-off cycles, the safety of the dailyx5 treatment with CPI-613 during pre-Cycle 1 will be evaluated in a dose-escalated manner in Cohorts 2-4.

6.2 Dosing Delay and Dose Modification of CPI-613 in the Event of Adverse Events

For adverse events unrelated to serum creatinine elevation or reduction in renal function but are possibly related to CPI-613, the occurrence of Grade 1 toxicity does not generally require dose modification for subsequent doses for that patient. However, if Grade 2 toxicity (other than alopecia and nausea) probably related to CPI-613 develops, treatment is to be withheld and can resume only after the Grade 2 toxicity has been reduced to Grade 1 or below, and the dose level for subsequent doses for that patient will be reduced by 25% of the dose at which such Grade 2 toxicity occurs. Grade 2 alopecia and nausea do not require withholding treatment or dose reduction. If Grade 3 or 4 toxicity probably related to CPI-613 develops, dosing of CPI-613 of that patient will be withheld and the patient shall be monitored for recovery from, and reversibility of, such Grade 3 or 4 toxicity. To resume treatment with CPI-613 for a patient who has had CPI-613-related Grade 3 or 4 toxicity, the Grade 3 or 4 toxicity must be reduced to Grade 1 or below, and the dose level for subsequent doses for that patient will be reduced to 50% of the dose at which such Grade 3 or 4 toxicity occurs.

For adverse events related to creatinine elevation or reduction in renal function that are possibly related to CPI-613, dosing of the patient will be withheld even if the severity level is Grade 2 or above. Treatment can resume only after the toxicity has been reduced to Grade 1. The dose level for subsequent doses for that patient will be reduced by 15% if the severity level is of Grade 1, by 25% for Grade 2 toxicity, and by 50% for Grade 3 or 4 toxicity.

Furthermore, if the toxicity possibly related to CPI-613 is acute renal failure and the severity level is Grade 3 or 4, further patient enrollment will be temporarily suspended in order to enable assessment of the following aspects of the trial and implementation of corrective measures or protocol amendment, and if necessary:

- compliance of the study sites and investigators to the study protocol
- evaluation of the appropriateness of the procedures for monitoring renal function

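### A Cohort 1 failure at 2,300 mg/m² lowers the cycle dose but sets no limit on the loading ladder, which can still reach 2,300 and then 3,000 mg/m²/day for 5 days

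*Combined protocol and SAP*

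**What the plan says.** Cohort 1 (Section 6.1.1) gives 2,300 mg/m² on Days 1 and 4 for three weeks of a four-week cycle, with no loading week. At the second DLT that dose "is considered to be above the maximum tolerated dose (MTD) for the 3-weeks-on-1-week-off treatment cycles", and the stated consequence is that "all subsequent patients in this trial will be treated at 1,700 mg/m² for the 3-weeks-on-1-week-off treatment cycles".

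Every later cohort takes its cycle dose from Cohort 1. The loading doses (five daily infusions in the Pre-Cycle 1 week) are fixed in the text: 1,200 mg/m²/day in Cohort 2, 1,700 in Sub-Cohort 2, 2,300 in Cohort 3 and 3,000 in Cohort 4. Movement up the ladder is governed as follows:

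- Cohort 2, no DLT in 3: "If none of these 3 patients develop a DLT, the study can move onto Cohort 3".
- Cohort 2, one DLT in 6: "Sub-Cohort 2 is activated only if 1 out of 6 patients exhibits DLT in Cohort 2".
- For Cohort 3, entry is stated thus: "This cohort will be performed only if DLT is observed in Cohort 2, or DLT is observed in 1 or less patients"; the second clause concerns Sub-Cohort 2. The first clause looks like a slip for no DLT, given the Cohort 2 text. On either reading it does not mention Cohort 1.
- Cohort 4: at most one DLT in Cohort 3.

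A loading dose that produces two DLTs "is considered to be above the MTD for the pre-Cycle 1 week", so the loading week has its own MTD. After two DLTs in Sub-Cohort 2: "In this case, the dose of CPI-613 for the pre-Cycle 1 week in subsequent patients in this trial will be 600 mg/m²/day". After two DLTs in Cohort 4 the loading dose reverts to 2,300 mg/m²/day. Section 9.0 repeats the scheme without any added link to Cohort 1.

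**The concern.** Section 6.1.2 presents Cohort 1 as the safety step that comes before escalation, and expects 2,300 mg/m² to be safe because its peak concentration is about 90 µM against about 200 µM at 3,000 mg/m². Two DLTs in Cohort 1 would undercut that premise. Yet the only written response is a lower cycle dose. The loading ladder keeps its top two rungs, at the same and at a higher dose per infusion, and given five days running instead of twice a week.

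The protocol does reason from one schedule to the other elsewhere. It justifies the 600 mg/m²/day fallback as 3,000 mg/m² per week, equal to the single-dose MTD. The starting loading dose fits the same logic: 5 × 1,200 = 6,000 mg/m² per week, which equals 2 × 3,000, the weekly total at the stated cycle MTD. So the separate MTDs do not by themselves explain why a Cohort 1 failure has no bearing on the loading dose.

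At stake is the exposure of patients in Cohorts 3 and 4 and, if Cohort 3 passes, of the ten analysed patients in Cohort 5, who would then receive 2,300 or 3,000 mg/m²/day.

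**Working it through.** **The plan's own figure.** Section 9.0 states 16 to 40 patients. Five escalation cohorts of at most 6, plus 10, give 5 × 6 + 10 = 40. Two cohorts of 3, plus 10, give 16 (read literally, stopping after 2 patients in each of two cohorts gives 14). The ladder as read here reproduces the stated range.

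**Exposure.** Inputs: cycle infusions on Days 1 and 4 of three weeks (6 per cycle); 5 loading infusions; DLT window through Cycle 1; cycle dose 1,700 mg/m² after a Cohort 1 failure, so Cycle 1 adds 6 × 1,700 = 10,200 mg/m². All doses are in mg/m², with the ratio to the failed schedule in parentheses.

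| Regimen | Highest single infusion | Heaviest week | Through Cycle 1 |
|---|---|---|---|
| Failed Cohort 1 | 2,300 | 2 × 2,300 = 4,600 | 6 × 2,300 = 13,800 |
| Cohort 2 | 1,700 (0.74) | 5 × 1,200 = 6,000 (1.30) | 16,200 (1.17) |
| Sub-Cohort 2 | 1,700 (0.74) | 5 × 1,700 = 8,500 (1.85) | 18,700 (1.36) |
| Cohort 3 | 2,300 (1.00) | 5 × 2,300 = 11,500 (2.50) | 21,700 (1.57) |
| Cohort 4 | 3,000 (1.30) | 5 × 3,000 = 15,000 (3.26) | 25,200 (1.83) |

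**Cumulative dose.** Loading is given once and cycles repeat. After n cycles the failed schedule gives 13,800n and Cohort 3 gives 11,500 + 10,200n. Cohort 3 is lower once 3,600n > 11,500, that is from cycle 4. Cohort 4 (15,000 + 10,200n) is lower once 3,600n > 15,000, from cycle 5. At 12 cycles the ratios are 133,900/165,600 = 0.81 and 137,400/165,600 = 0.83.

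**Likelihood.** The documents give no DLT rates, so every rate here is an assumption. With DLT probability p and q = 1 − p, a cohort passes with probability Pass(p) = q³ + 3pq⁵. The chance that Cohort 1 fails, 1 − Pass(p), is 0.027, 0.094, 0.291, 0.506 and 0.691 at p = 0.05, 0.1, 0.2, 0.3 and 0.4. Cohort 3 then opens with probability q₂³ + 3p₂q₂⁵ × Pass(p of Sub-Cohort 2), and Cohort 4 with that times Pass(p of Cohort 3).

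| Cohort 1 rate | Cohort 2 / Sub-Cohort 2 / Cohort 3 rates | Cohort 1 fails and Cohort 3 opens | Cohort 1 fails and Cohort 4 opens |
|---|---|---|---|
| 0.1 | 0.05 / 0.10 / 0.20 | 0.090 | 0.064 |
| 0.2 | 0.10 / 0.20 / 0.35 | 0.249 | 0.099 |
| 0.3 | 0.20 / 0.30 / 0.40 | 0.308 | 0.095 |
| 0.4 | 0.30 / 0.40 / 0.50 | 0.269 | 0.046 |
| 0.1 | 0.1 / 0.2 / 0.3 | 0.080 | 0.040 |
| 0.2 | 0.2 / 0.3 / 0.4 | 0.178 | 0.055 |
| 0.3 | 0.3 / 0.4 / 0.5 | 0.197 | 0.034 |
| 0.4 | 0.4 / 0.5 / 0.6 | 0.160 | 0.013 |

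At a Cohort 1 rate of 0.05 the joint chance cannot exceed 0.027, whatever follows. Neither end of the range is a bound: a Cohort 1 rate of 0.3 with 0.1 in both Cohort 2 and Sub-Cohort 2 gives 0.45.

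**Patients affected.** If Cohort 4 opens, 3–6 (Cohort 3) + 2–6 (Cohort 4) + 10 (Cohort 5) = 15–22 patients receive at least 2,300 mg/m²/day.

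**The case against.** Several points on the other side stand.

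A reader might infer that the rules contradict each other, or that Cohort 3 gives a dose already declared too toxic. They do not: the Cohort 1 finding is limited to the cycle schedule, and the loading week has its own MTD. A reader might also infer that the Cohort 1 result is ignored altogether. It is not: the cycle dose falls to 1,700 mg/m² for everyone, which takes Cycle 1 from 13,800 to 10,200 mg/m². Nor are the later regimens heavier on every measure, because cumulative dose is lower from cycle 4 or 5.

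The branch may also be unlikely. Section 6.1.2 describes 2,300 mg/m² as below the MTD on this same schedule and reports no significant adverse effects at or below the MTD. Cohort 3 opens only after patients have tolerated a loading week at 1.3 or 1.85 times the failed weekly total. Cohort 5 receives 2,300 mg/m²/day or more only after 3 to 6 patients had at most one DLT at 2,300 mg/m²/day loading, which is more direct evidence than Cohort 1. Moving to Cohort 3 is worded as permission. The Safety and Toxicity Review Committee can suspend the trial, Grade 3–4 acute renal failure suspends enrolment, and the sponsor can terminate. Section 9.0 says the FDA discussed or proposed the scheme.

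These points limit the concern without removing it. The stop at the second DLT and the Section 6.2 reductions act after exposure. The committee is notified only of unexpected Grade 4 and all Grade 5 events. No DLT in 3 patients at 1,200 mg/m²/day is weak reassurance about 2,300: at a true rate of 0.3 it happens 34% of the time (0.7³). FDA discussion does not show that this branch was examined. Section 6.0 does say that in both phases "patients will be treated with CPI-613 at the same dose, unless dose modification is warranted", but this cannot serve as a cap, because Cohort 2 pairs 1,200 mg/m² loading with a different cycle dose. The jump from 1,200 to 2,300 exists whether or not Cohort 1 fails and is a separate matter.

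**Conclusion.** The gap is real and contingent. After a Cohort 1 failure the written rules lower the cycle dose but leave the loading ladder open to 2,300 and 3,000 mg/m²/day for five days. Short-term exposure is then 2.5 and 3.3 times the failed schedule by weekly total, and 1.57 and 1.83 times over the DLT window. These ratios follow from the stated doses and need no assumption beyond counting the loading week within the DLT window. The chance of reaching Cohort 3 by this route (under 3% at an assumed Cohort 1 rate of 0.05, about 31% at 0.3 with 0.2 in Cohort 2) rests wholly on assumed rates. The point lies between minor and should-fix: a cheap safety improvement to a branch that the protocol itself expects not to occur.

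**What to change.** Add to both Section 6.1.1 and Section 9.0: *If 2,300 mg/m² is declared above the MTD in Cohort 1, Cohorts 3 and 4 do not open and the Pre-Cycle 1 dose may not exceed 1,700 mg/m²/day.* In that branch only:

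- Cohort 2 at 0 of 3 or 1 of 6 leads to Sub-Cohort 2, as an exception to the present activation sentence.
- At most one DLT in Sub-Cohort 2 opens Cohort 5 at 1,700 mg/m²/day, instead of Cohort 3.
- Two DLTs in Cohort 2 or in Sub-Cohort 2 keep the existing 600 mg/m²/day fallback. A fallback to 1,200 mg/m²/day after 0 of 3 in Cohort 2 is not advised: it would be double the 600 already prescribed after a Sub-Cohort 2 failure, and would rest on three patients.

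Nothing changes when Cohort 1 passes.

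Cost: one conditional paragraph in two sections, by amendment, to a scheme that the protocol says was discussed with or proposed by the FDA. In this branch maximum enrolment falls from 40 to 3 × 6 + 10 = 28. The path with no loading DLTs falls from 21–25 patients (2–6 + 3 + 3 + 3 + 10) to 18–22 (2–6 + 3 + 3 + 10). Loading doses above 1,700 mg/m²/day would not be explored there, including after a chance Cohort 1 failure (9% at a true DLT rate of 0.1, 29% at 0.2). The cap keeps each infusion below the dose that failed, but short-term totals stay above the failed schedule, by up to 1.85 times weekly and 1.36 times over the DLT window. Those levels remain under their own DLT rules.

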Cohort 2: In another 3 patients, the dose of CPI-613 for the 3-weeks-on-1-week-off treatment cycles will be as determined from Cohort 1. These patients will also be treated with the 5 daily doses of CPI-613 during the pre-Cycle 1 week. The dose of CPI-613 for the pre-Cycle 1 week will be 1,200 mg/m²/day, which has previously been established to be the weekly MTD (see Section 6.1.2). If none of these 3 patients develop a DLT, the study can move onto Cohort 3.

However, if a DLT is observed in a patient (whether it is the 1st, 2nd or 3rd of the 3 intended patients), the number of patients in this cohort will be expanded to a maximum of 6 patients. If no DLT is observed in another patient out of a maximum of 6 patients, the study will move onto Sub-Cohort 2 (see below). However, if a DLT is observed in 2 patients, no additional patients will be treated at 1,200 mg/m²/day during the pre-Cycle 1 week even though the total number of patients at this cohort is as few as 2. The dose level of 1,200 mg/m²/day during the pre-Cycle 1 week, which induces a DLT in 2 or more patients, is considered to be above the MTD for the

Comprehensive Cancer Center of Wake Forest University
A Pilot Study: Open-Label Clinical Trial of CPI-613 in Patients with Advanced Bile Duct
Cancers
CCCWFU # 59212

pre-Cycle 1 week. In this case, the dose of CPI-613 for the pre-Cycle 1 week in subsequent patients in this trial will be 600 mg/m²/day (or 3,000 mg/m²/week, equivalent to the MTD when given as a single dose).

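### Two DLTs in Cohort 2 are charged only to the Pre-Cycle 1 dose, although Cohort 2 can also be the first cohort given 3,000 mg/m² cycles and one DLT count covers both

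*Combined protocol and SAP*

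**What the plan says.** Section 6.1.1 gives Cohort 1 treatment cycles at 2,300 mg/m² and no Pre-Cycle 1 week. If there is no DLT in three patients, or only one in six, "the dose for the 3-weeks-on-1-week-off treatment cycles will be 3,000 mg/m² in all subsequent patients in this trial". Cohort 2 takes that cycle dose and adds five daily infusions of 1,200 mg/m². A single window serves both parts: "The DLT determining period for all cohorts in the dose-escalation scheme is through the first cycle". Section 6.1.1 counts Grade 3 or higher toxicity that is probably or definitely related to CPI-613, while Section 9.0 states the grade only. Neither definition asks which part of the regimen was responsible.

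If two Cohort 2 patients have a DLT, the rule says that the 1,200 mg/m²/day dose, "which induces a DLT in 2 or more patients, is considered to be above the MTD for the pre-Cycle 1 week", and that "the dose of CPI-613 for the pre-Cycle 1 week in subsequent patients in this trial will be 600 mg/m²/day". Section 9.0 carries the same rule ("The dose level of 1,200 mg/m²/day during the pre-Cycle 1 week, which induces a DLT in 2 or more patients"). For Cohort 5, the ten-patient analysis group, "the dose of CPI-613 for the 3-weeks-on-1-week-off treatment cycles will be as determined from Cohort 1".

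The justification is in Section 6.1.2. Citing Phase I trials in solid tumours and haematologic malignancies, it states that the 3,000 mg/m² level "is the MTD, when CPI-613 is given as a single agent infused over 2 hours on Days 1 and 4 for 3 weeks". On tolerability it adds: "CPI-613 did not induce any significant adverse effects at or below MTD".

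**The concern.** A dose-finding step supports a conclusion about one component only if that component is what changed, or if something else identifies the cause. When Cohort 1 clears, two components change on entry to Cohort 2, and the rule names one of them as the culprit. No cohort receives 3,000 mg/m² cycles without the lead-in, so the trial has no observation of its own to fall back on.

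If the cycle dose is in fact the source, one of two things happens. Where its DLT rate is one the scheme would tolerate, the lead-in is halved for no reason and the levels from 1,700 to 3,000 mg/m²/day are not explored. Where its DLT rate is about one third or more, a cycle dose the scheme would itself reject goes forward to the ten patients who supply the response and safety estimates, and the description of them in Section 9.0 as treated at the MTD would not fit.

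**Working it through.** **Check that the scheme is read correctly.** Five escalation cohorts (1, 2, Sub-Cohort 2, 3, 4) of at most six, plus ten, give 5 × 6 + 10 = 40. This is the maximum stated in Section 9.0. The documents give no DLT rates.

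**What each cohort changes, if Cohort 1 clears (Section 6.1.1).**

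| Cohort | Pre-Cycle 1, mg/m²/day × 5 | Cycle dose, mg/m² | New in this trial |
|---|---|---|---|
| 1 | none | 2,300 | cycles |
| 2 | 1,200 | 3,000 | both parts |
| Sub-Cohort 2 | 1,700 | 3,000 | lead-in level only |
| 3 | 2,300 | 3,000 | lead-in level only |
| 4 | 3,000 | 3,000 | lead-in level only |
| 5, after two DLTs in Cohort 2 | 600 | 3,000 | lead-in level only |

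**Dose inside the DLT window.** A cycle has six infusions.
- Cohort 1: 6 × 2,300 = 13,800 mg/m².
- Cohort 2: 5 × 1,200 + 6 × 3,000 = 24,000 mg/m², of which 18,000 / 24,000 = 75% is cycle dosing.
- After the fallback: 5 × 600 + 6 × 3,000 = 21,000 mg/m², a cut of 3,000 / 24,000 = 12.5%, all of it in the lead-in.

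Section 6.1.2 puts peak plasma concentration at about 90 µM for 2,300 mg/m² and about 200 µM for 3,000 mg/m². The cycle dose rises by a factor of 3,000 / 2,300 = 1.3 and the peak by about 200 / 90 = 2.2, so the cycle step is not negligible.

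**Chance that a cohort fails.** With DLT probability p and q = 1 − p, a cohort passes with no DLT in three, or with one in the first three and none in the next three. Hence P(fail) = 1 − [q³ + 3pq² × q³].

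| Assumed p | 10% | 16.7% | 20% | 25% | 33.3% | 40% |
|---|---|---|---|---|---|---|
| P(fail) | 0.09 | 0.22 | 0.29 | 0.40 | 0.57 | 0.69 |

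**Three causes, one count.** Assume the two parts act independently, so that total p = 1 − (1 − p_cycle)(1 − p_pre).
- Cycle 33.3%, lead-in 0: total 33.3%, P(fail) 0.57. The rule lowers the wrong part.
- Cycle 0, lead-in 33.3%: total 33.3%, P(fail) 0.57. The rule is right.
- Cycle 20%, lead-in 16.7%: 1 − 0.80 × 0.833 = 33.3%, P(fail) 0.57. If the lower lead-in removed its whole share, 20% would remain, below the 2 in 6 that the scheme rejects. The rule's action is then defensible.

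**Including the condition that Cohort 1 clears.** If the DLT rate at 2,300 mg/m² is 10% or 20%, Cohort 1 clears with probability 1 − 0.094 = 0.906 or 1 − 0.291 = 0.709. Clearing and then failing Cohort 2 at 33.3% has probability 0.906 × 0.572 = 0.52 or 0.709 × 0.572 = 0.41.

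**Do other provisions correct the conclusion?**
- Section 6.2 changes doses for the affected patient only: 3,000 × 0.75 = 2,250 mg/m² after Grade 2 toxicity and 3,000 × 0.50 = 1,500 mg/m² after Grade 3 or 4, when probably related and not renal.
- The enrolment pause in 6.2 applies to Grade 3 or 4 acute renal failure only.
- Section 8.3 requires reported unanticipated risks to be reviewed for a possible protocol change. The Safety and Toxicity Review Committee can suspend the trial, but Table 1 of Appendix B does not require Grade 3 events to be reported to it.
- Appendix C records start date and cycle of onset, but no escalation rule uses them.

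None of these is triggered by every two-DLT cohort.

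**The case against.** The strongest reply is that the attribution rests on prior evidence. Section 6.1.2 gives 3,000 mg/m² as the MTD on the same Day 1 and Day 4 schedule, so the new five-day course is the natural suspect. The scheme fixes the cycle dose first and then varies the lead-in, so its MTD can be read as the lead-in MTD at that cycle dose. If the parts act together, lowering the lead-in is a legitimate response. Section 6.1.1 also calls 1,200 mg/m²/day an established weekly MTD, and 5 × 1,200 = 6,000 mg/m² equals the weekly total of 2 × 3,000. Section 9.0 says the scheme was discussed with or proposed by the FDA.

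Most of this stands, and it makes blaming the lead-in a reasonable first guess. It does not make the guess a finding. The Phase I evidence comes from other malignancies and describes no preceding five-day course. Section 1 says the drug had not been studied in cholangiocarcinoma. The claimed support for 1,200 mg/m²/day, if accepted, helps both parts equally and does not single out the lead-in.

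The reply is also right about the arithmetic. Equal total rates give equal failure probabilities by construction, so the figures show that the count is blind to cause, not how often the rule errs. A reader might go further and infer that 3,000 mg/m² is too toxic, or that misattribution would cause 3.3 or 4.0 DLTs in Cohort 5 at cycle rates of 33% or 40%. The documents support neither. No such rate appears in them, those counts are ten times an assumed rate, and Cohort 5 would receive 3,000 mg/m² cycles even if Cohort 2 passed. Nor does the problem extend to Sub-Cohort 2 or Cohorts 3 and 4, where only the lead-in level changes.

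**Conclusion.** The point holds in a limited form. If Cohort 1 clears and Cohort 2 then has two DLTs, the data show that the combination of 1,200 mg/m²/day and 3,000 mg/m² cycles is above the MTD. They do not show that the lead-in alone is. The prescribed action is right if the lead-in is the cause, defensible if the combination is, and wrong only if the cycle dose alone, or the cycle toxicity left after the lead-in is lowered, drives the DLTs.

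The harm is minor to moderate. It needs three conditions together: Cohort 1 clears, Cohort 2 has two DLTs, and the cycle dose is materially responsible. If Cohort 1 fails, cycles drop to 1,700 mg/m² and the concern is smaller. All DLT rates used here, and the independence of the two parts, are assumptions. The change is worth making because it is cheap and bears on both the stated conclusion and the next dosing decision.

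**What to change.** In Sections 6.1.1 and 9.0:

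1. State that two DLTs in Cohort 2 show the combination of the current Pre-Cycle 1 dose and cycle dose to be above the MTD. Describe Cohort 5 as treated at the selected combined regimen.
2. Report DLTs by onset before or after the first Cycle 1 infusion.
3. If Cohort 2 has two DLTs and at least one began after the first Cycle 1 infusion, require a documented review before the next patient is enrolled. It should decide whether to keep or lower the 3,000 mg/m² cycle dose, and consider the Pre-Cycle 1 dose alongside it. No automatic step-down is needed.

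The cost is wording in two mirrored sections and, at most, one review. No patients, visits or tests are added: the Appendix C log already holds start date, cycle of onset and DLT status, and Section 5.1.2 already schedules safety tests on Day 5 of Pre-Cycle 1 and before each cycle. At the planned one patient per month, a review finished within a month delays about one enrolment. Onset is an imperfect guide, because late lead-in toxicity can appear in Cycle 1 and four of the five weeks in the window belong to Cycle 1. The trigger should therefore prompt judgement, not decide the dose.
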